10.4 Vital Sign Data

For each vital sign parameter (by position for blood pressure and pulse rate), descriptive statistics of actual measurements and changes from baseline at each time point and the last assessment time point (Week 52 LOCF) will be calculated.

Numbers and proportions of subjects with vital signs meeting the criteria for potentially clinically significant vital signs (Appendix 1) will be determined. A listing of these subjects will be provided.

10.5 Physical Examination Data

Physical examination data will be provided in a listing.

10.6 Electrocardiogram Data

For heart rate, PR interval, RR interval, QRS interval, QT interval, and QT corrected for heart rate (QTc), descriptive statistics of actual measurements and changes from baseline at each time point and the last assessment time point (Week 52 LOCF) will be calculated.

A shift table from baseline for normal/abnormal 12-lead electrocardiogram (ECG) (evaluated at the trial site) will be produced.

Numbers and proportions of subjects with actual measurements of QTc (QTcF, QTcB, QTcN) not meeting the criteria of > 450 msec, > 480 msec, and > 500 msec at baseline and meeting the criteria after treatment will be determined. Numbers and proportions of subjects with changes from baseline of > 30 msec and > 60 msec will be determined.

Numbers and proportions of subjects with actual measurements of > 450 msec with a % change from baseline of $> 10\%$ will be determined.

Numbers and proportions of subjects with ECG results meeting the criteria for potentially clinically significant ECG data (Appendix 3) will be determined. A listing of these subjects will be provided.

10.7 Other Safety Data

10.7.1 Body Weight, BMI, and Waist Circumference

For body weight, BMI, and waist circumference, descriptive statistics of actual measurements and changes from baseline at each time point and the last assessment time point (Week 52 LOCF) will be calculated.

Numbers and proportions of subjects with results meeting the criteria for potentially clinically significant body weight gain or loss (Appendix 1) will be determined. Body weight data will also be analyzed by baseline BMI category (< 18.5 , ≥ 18.5 to < 25 , ≥ 25 to < 30 , ≥ 30) in a similar manner. A listing of subjects with results meeting the criteria for potentially clinically significant body weight gain or loss (Appendix 1) will be provided.

10.7.2 DIEPSS, AIMS, and Barnes Akathisia Rating Scale (BARS)

For DIEPSS total score (total of scores for items 1 through 8) and the score for each DIEPSS item, AIMS total score (total of scores for items 1 through 7) and the score for each of the items 8 through 10, and BARS, descriptive statistics of actual measurements and changes from baseline at each time point and the last assessment time point (Week

52 LOCF) and the worst postdose measurement and its change from baseline will be calculated.

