### **1.3 Known and Potential Risks and Benefits**

Extrapyramidal symptoms, seizures, suicidality, and dyslipidemia have been assessed as important risks associated with the administration of brexpiprazole. The potential mechanism of antipsychotics causing seizures is a class effect thought to be due to a reduction of the seizure threshold in susceptible individuals. The occurrence of suicidal behavior is inherent in psychotic illnesses and mood disorders. In the schizophrenia and major depressive disorder populations, short-term and long-term administration of brexpiprazole was associated with moderate weight gain; however, weight gain did not contribute significantly to IMP discontinuation, and only a few subjects with marked weight gain demonstrated metabolic syndrome. Although not clinically significant, an increase in triglycerides was observed in some trials. Due to this observation and considerations on potential clinical consequences related to weight gain, dyslipidemia is considered to be an important potential risk.

With lower intrinsic activity at the D2 receptors and more potent effects on the serotonergic system, which is suggested to be involved in the improvement of depressive symptoms, extrapyramidal symptoms, and cognitive function, compared with aripiprazole, evidence suggests that brexpiprazole can reduce the incidence of AEs such as akathisia and other extrapyramidal symptoms, nausea, vomiting, excitement, and irritability, and also improve symptoms of depression. In clinical trials conducted overseas, the incidence of AEs, such as akathisia, which are considered risk factors for low adherence to treatment, was confirmed to be low in patients treated with brexpiprazole. Therefore, brexpiprazole is likely to become a useful treatment option for patients with major depressive disorder who need to receive treatment over a long period of time.

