## 4.3 Restricted Concomitant Drugs

The use of the following drugs is restricted during the treatment period.

- Ultrashort-acting sedative-hypnotic drugs  
Ultrashort-acting sedative-hypnotic drugs that can be used in this trial are restricted to zolpidem, zopiclone, eszopiclone, and triazolam. The concomitant use of only one of the aforementioned drugs is allowed during the treatment period; 2 or more drugs are not to be coadministered simultaneously. Change in the types of the aforementioned drugs is allowed.
- Anticholinergic drugs for Parkinson's disease  
Anticholinergic drugs for Parkinson's disease, for which concomitant use during the treatment period is allowed, are biperiden, trihexyphenidyl, profenamine, piroheptine,

and mazaticol. In the case where extrapyramidal symptoms occur and use is necessary in the opinion of the investigator or subinvestigator, only one drug can be coadministered with no prophylactic use allowed. Change in the types of the aforementioned drugs is allowed.

- Antipyretic analgesic anti-inflammatory drugs, antihistamines  
Concomitant use is allowed if subjects were already using the drugs at the time of informed consent to treat complications; however, no changes in dose and regimen are allowed unless AEs occur or the use of these drugs is considered unnecessary because of remission of symptoms. Furthermore, short-term concomitant use, including use as a medication for colds during the treatment period, is also allowed. The topical external use of these drugs is allowed.  
Note: Caution should be exercised to avoid concomitant use of CYP2D6 inhibitors, CYP3A4 inhibitors, and CYP3A4 inducers specified in Section 4.4 Other Restrictions (eg, chlorpheniramine, diphenhydramine, clemastine, and celecoxib).
- $\beta$ -Blockers  
During the treatment period, use is allowed only for treatment of cardiovascular diseases, with no changes in the dose and regimen employed at the time of informed consent. The topical external use of these drugs is allowed.

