7.2 Demographic and Baseline Characteristics

Descriptive statistics (mean, standard deviation, minimum, median, maximum; hereinafter the same applies) of age, height, body weight, waist circumference, and body mass index (BMI) and frequency distribution of sex, race, ethnicity, country where trial is conducted, medical history, and complications will be determined in each analysis set. Similar summarization will be performed for each requisite concomitant medication.

In rollover subjects, baseline data in the present trial will be used for body weight, waist circumference, and BMI. For medical history and complications, baseline data in the present trial as well as in the double-blind trial (331-102-00058) will be used. For the other demographic characteristics, baseline data in the double-blind trial (331-102-00058) will be used.

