CT-10.4.1	Potential Hy's Law Cases (Safety Analysis Set)
CT-10.4.2	Listing of Potential Hy's Law Cases (Safety Analysis Set)

- CT-10.5.1 Incidence of Laboratory Test Values With Potential Clinical Relevance - Prolactin (Safety Analysis Set)
- CT-10.5.2 Listing of Laboratory Test Values With Potential Clinical Relevance - Prolactin (Safety Analysis Set)
- CT-10.6.1 Incidence of Treatment-emergent Significant Change in Lipids (Safety Analysis Set)
- CT-10.6.2 Listing of Treatment-emergent Significant Change in Lipids (Safety Analysis Set)
- CT-10.7.1 Incidence of Treatment-emergent Significant Change in Glucose (Safety Analysis Set)
- CT-10.7.2 Listing of Treatment-emergent Significant Change in Glucose (Safety Analysis Set)
- CT-10.8.1 Incidence of Treatment-emergent Metabolic Syndrome (Safety Analysis Set)
- CT-10.8.2 Listing of Treatment-emergent Metabolic Syndrome (Safety Analysis Set)
- CT-11.1 Mean Change From Baseline in Vital Signs (Safety Analysis Set)
- CT-11.2 Incidence of Potentially Clinically Relevant Abnormalities in Vital Signs (Safety Analysis Set)
- CT-11.3 Listing of Potentially Clinically Relevant Abnormalities in Vital Signs (Safety Analysis Set)
- CT-11.4 Summary of Mean Change From Baseline in Body Weight (kg) (Safety Analysis Set)
- CT-11.5 Summary of Mean Change From Baseline in Waist Circumference (cm) (Safety Analysis Set)
- CT-11.6 Summary of Mean Change From Baseline in BMI (kg/m²) (Safety Analysis Set)
- CT-11.7 Incidence of Potentially Clinically Relevant Weight Gain or Loss by Baseline BMI (Safety Analysis Set)
- CT-12.1 Mean Change From Baseline in ECG Results (Safety Analysis Set)
- CT-12.2 Shift Tables of ECG (Safety Analysis Set)
- CT-12.3 Incidence of Categorical Changes in QT/QTc (Safety Analysis Set)
- CT-12.4 Incidence of Potentially Clinically Relevant Abnormalities in ECG Evaluations (Safety Analysis Set)
- CT-12.5 Listing of Potentially Clinically Relevant Abnormalities in ECG Evaluations (Safety Analysis Set)
- CT-13.1 Summary of Mean Change From Baseline in DIEPSS (Safety Analysis Set)
- CT-13.2 Summary of Mean Change From Baseline in AIMS Total Score and Item Scores 8, 9 and 10 (Safety Analysis Set)
- CT-13.3 Summary of Mean Change From Baseline in BARS, Global Clinical Assessment of Akathisia (Safety Analysis Set)
- CT-14.1 C-SSRS, Suicidality (Safety Analysis Set)
- CT-14.2 C-SSRS, Suicidal Behavior by Type (Safety Analysis Set)
- CT-14.3 C-SSRS, Suicidal Ideation by Type (Safety Analysis Set)

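### DIEPSS, AIMS and BARS are summarised only as continuous scores, so no table shows how many subjects' scale scores became abnormal or worsened

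*SAP*

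**What the plan says.** SAP 10.7.2 covers the DIEPSS total and item scores, the AIMS total and items 8 to 10, and BARS. For these it asks for descriptive statistics, both of the scores and of their changes, by visit and at the last assessment. It then adds a summary of each subject's worst score: "52 LOCF) and the worst postdose measurement and its change from baseline will be calculated". SAP 7.2 fixes the meaning of descriptive statistics for the rest of the plan: "Descriptive statistics (mean, standard deviation, minimum, median, maximum; hereinafter the same applies".

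Appendix 5 lists one summary table per scale, CT-13.1 (DIEPSS), CT-13.2 (AIMS) and CT-13.3 (BARS). All three carry a mean-change title; the last is "Summary of Mean Change From Baseline in BARS, Global Clinical Assessment of Akathisia (Safety Analysis Set". AIMS items 1 to 7 enter only through their total. Subject-level scores appear in listings PDATA-11 to PDATA-13.

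Adverse events are handled separately. SAP 10.2.1 counts subjects with extrapyramidal events by SOC and PT. The Appendix 4 term list includes akathisia, dyskinesia and tardive dyskinesia, and the table is CT-8.9.1.

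Protocol 1.3 gives the reason to care: "Extrapyramidal symptoms, seizures, suicidality, and dyslipidemia have been assessed as important risks associated with the administration of brexpiprazole".

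**The concern.** The clinical question about akathisia or dyskinesia is how many subjects developed it. A mean or median score does not answer that when few subjects are affected: the few high scores are spread over the whole group, and improvement in some subjects can offset worsening in others. The scheduled ratings are a structured source that does not depend on a subject volunteering a complaint. If they are reported only as continuous scores, the clinical study report will carry no scale-based incidence for a named important risk. A reader would have to build one from the listings.

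**Working it through.** **1. How the SAP treats its other safety measures.**
- Laboratory values (10.3, Appendix 2): n (%) not meeting the criterion at baseline and meeting it after treatment.
- QTc (10.6): n (%) newly above 450, 480 and 500 msec.
- Vital signs (10.4, Appendix 1): n (%) meeting a criterion value together with a minimum change from baseline.
- Weight (10.7.1, Appendix 1): n (%) with a gain or loss of at least 7%.
- C-SSRS (10.7.3): n (%) with emergence or worsening.
- DIEPSS, AIMS, BARS (10.7.2): no threshold, shift table or n (%). Appendices 1 to 3 have no entry for them.

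**2. A figure to reproduce.** There is none. The targets of about 100 completers and 30 elderly subjects (SAP section 4) come with no precision or power statement. What follows is illustration.

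**3. Dilution.** Inputs: akathisia AE rates of 8.3% (overseas elderly trial, Protocol 1.2.2.5) and 6.7% (overseas long-term trial, Protocol 1.2.2.4). The BARS global item is rated on a 6-point scale (Protocol 3.7.4.9), taken here to start at 0. Assumptions not in the documents: each case scores s, and everyone else scores 0. Then mean = k × s / N.
- N = 30: 30 × 0.083 = 2.49, taken as k = 2. With s = 2, 2 × 2 / 30 = 0.13 (SD 0.51). With s = 3, 2 × 3 / 30 = 0.20 (SD 0.76). The median is 0; the maximum is 2 or 3.
- N = 100: 100 × 0.067 = 6.7, taken as k = 7. With s = 1, 2, 3 the mean is 7 × s / 100 = 0.07, 0.14, 0.21, and the median is 0.

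At least one case is likely at these rates: 1 − (1 − 0.083)^30 = 92.6%, and 1 − (1 − 0.067)^100 = 99.9%.

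**4. Cancellation.** If 7 of 100 subjects worsen by 2 points and 14 improve by 1, the mean change is (7 × 2 − 14 × 1) / 100 = 0.00.

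**5. Whether the five statistics together recover the count.** In general they do not. A maximum of 3 is the same for one subject or seven. As a constructed example with N = 30 and all other scores 0, compare worst scores {3, 3, 1, 1, 1} with {3, 2, 2, 2}. Both sum to 9 (mean 9 / 30 = 0.30). Both have a sum of squares of 21, so SD = √[(21 − 81/30) / 29] = 0.79. Both have minimum 0, median 0 and maximum 3. The first set has 2 subjects at 2 or above and the second has 4.

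**6. What a count would show.** 2 of 30 is 6.7% (exact 95% CI 0.8% to 22.1%). 7 of 100 is 7.0% (2.9% to 13.9%).

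**The case against.** The strongest reply is that the plan already does more than the table titles suggest. A reader might infer from those titles that the scales are summarised by means alone. They are not: SAP 7.2 includes SD, minimum, median and maximum, and 10.7.2 includes the worst value after dosing. So a group in which nobody is affected (maximum 0) can be told from one in which a few are. What cannot be read off is how many.

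A reader might also infer that nothing in the plan counts affected subjects. CT-8.9.1 does so for extrapyramidal TEAEs. The general TEAE tables also break events down by severity, discontinuation and time to first onset. The akathisia rates used above are AE rates, so cases arising at those rates are the kind CT-8.9.1 would report. This stands, and it narrows the gap. It does not close it, because AEs are elicited with one open question (Protocol 5.2) and CT-8.9.1 uses no scale score.

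A third inference is that anticholinergic treatment hides cases. Protocol 4.3 allows these drugs once symptoms occur; "only one drug can be coadministered with no prophylactic use allowed". Such treatment could lower later ratings and the Week 52 LOCF value, but not a worst score already recorded. DIEPSS is rated at every treatment visit. BARS and AIMS are rated only at baseline and Weeks 8, 24 and 52 (or discontinuation), so some peaks may fall between ratings. Use of these drugs during treatment is already tabulated by class in CT-4.1.2, so a separate row is not needed.

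**Conclusion.** The point holds in a limited form. For DIEPSS, AIMS and BARS the plan gives continuous summaries, including the worst value, and no count of subjects whose score became abnormal or worsened. The SAP provides counts of that kind for its other main safety measures. Under the stated assumptions, two affected elderly subjects out of 30 appear as a mean worst score of 0.13 to 0.20 with a median of 0, and the number affected cannot be recovered from the planned statistics.

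This rests on non-cases scoring 0, on case scores of 2 to 3, and on an AE rate standing in for a scale-based rate. The documents give no score distribution, and rollover subjects from the brexpiprazole group may start above 0. They also give no figure for cases that the scales would detect and AE reports would miss, so the information lost is real but not quantified. The documents do not support saying that extrapyramidal symptoms go uncounted. The gap is in reporting: the data are collected and listed.

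**What to change.** In SAP 10.7.2 and Appendix 5, add one of the following for each of the five analysis groups in SAP section 5:
- a shift table from baseline category to worst postdose category for the BARS global item, the DIEPSS items and the AIMS items; or
- the n (%) of subjects below a threshold at baseline and at or above it at the worst postdose value.

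The documents give no cut-offs for these scales, so the sponsor should set and justify the categories or thresholds before data lock. If lock has passed, the table should be labelled post hoc. Keep the continuous summaries, and read the counts beside CT-8.9.1 and CT-4.1.2. No count needs headline status, since SAP section 6 plans no primary or secondary outcome variables.

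The cost is a few extra tables and the choice of cut-offs in advance. No new assessments are needed.

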10.7.3 Columbia-Suicide Severity Rating Scale (C-SSRS)

Numbers and proportions of subjects for each C-SSRS item (suicidality, suicidal ideation, suicidal behavior, completed suicide, emergence of suicidal ideation, emergence of serious suicidal ideation, worsening of suicidal ideation, and emergence of suicidal behavior) at each time point and in the overall period after initiation of IMP treatment (including the post-treatment observation period, at discontinuation, and unscheduled visits) will be determined. A listing of subjects with emergence of suicidal ideation, emergence of serious suicidal ideation, worsening of suicidal ideation, and emergence of suicidal behavior will be provided. Items of suicidal ideation and suicidal behavior will also be summarized in the same manner.

- Suicidality: “Yes” for any item of suicidal ideation or suicidal behavior
- Suicidal ideation: “Yes” for any item of suicidal ideation
- Suicidal behavior: “Yes” for any item of suicidal behavior
- Emergence of suicidal ideation: Change from “No” at baseline to “Yes” after baseline for suicidal ideation
- Emergence of serious suicidal ideation: Change from “No” at baseline to “Yes” with Grade 4 or 5 after baseline for suicidal ideation
- Worsening of suicidal ideation: Increase in the grade of suicidal ideation from baseline
- Emergence of suicidal behavior: Change from “No” at baseline to “Yes” after baseline for suicidal behavior

11 Pharmacokinetic Analyses

Not applicable.

12 Pharmacodynamic Analyses

Not applicable.

13 Pharmacogenomic Analyses

Not applicable.

14 Interim Analysis

None.

15 Changes in the Planned Analyses

- The following changes were made to categorical analyses of QTc:
 - Only subjects with postdose QTc meeting the criteria will be summarized, instead of summarization at all time points.
 - Only subjects with QTc not meeting the criteria at baseline and meeting the criteria after baseline will be summarized.
- C-SSRS will be analyzed in the overall period after initiation of IMP treatment, not at the last assessment time point.

16 References

Not applicable.

17 History of Amendments

Table 17-1 History of Amendments		
Version	Date	Major Changes
1.0	01 Jun 2021	Not applicable
2.0	19 Jul 2022	
 Exclusion of subjects who did not comply with GCP was added to the definition of analysis sets in Section 5 Statistical Analysis Datasets. The wording “Agranulocytosis, neutropenia, leukopenia” was replaced with the more appropriate term “Blood disorder-related AEs” in Section 10.2.1 Adverse Events of Interest. A typographical error in Section 15 Changes in the Planned Analysis was corrected (before correction: “after initiation of after IMP treatment”; after correction: “after initiation of IMP treatment” (Please note that this error had been made only in the Japanese version and no correction was necessary in the English version.)

Appendix 1 Criteria for Identifying Vital Signs and Weight of Potential Clinical Relevance

Variable	Criterion Value ^a	Change Relative to Baseline ^a
Pulse Rate	> 120 bpm	≥ 15 bpm increase
	< 50 bpm	≥ 15 bpm decrease
Systolic Blood Pressure	> 180 mmHg	≥ 20 mmHg increase
	< 90 mmHg	≥ 20 mmHg decrease
Diastolic Blood Pressure	> 105 mmHg	≥ 15 mmHg increase
	< 50 mmHg	≥ 15 mmHg decrease
Orthostatic Hypotension	≥ 20 mmHg decrease in systolic blood pressure and a ≥ 25 bpm increase in pulse rate from supine to sitting/standing	Not Applicable
Weight	-	≥ 7% increase ≥ 7% decrease

^aIn order to be identified as potentially clinically relevant, an on-treatment value must meet the “Criterion Value” and also represent a change from the subject’s baseline value of at least the magnitude shown in the “Change Relative to Baseline” column.

Appendix 2 Criteria for Identifying Laboratory Values of Potential Clinical Relevance

Laboratory Tests		Criteria
Chemistry		
AST (SGOT)	$\geq 3 \times$ upper limit of normal (ULN)	
ALT (SGPT)	$\geq 3 \times$ ULN	
Alkaline phosphatase	$\geq 3 \times$ ULN	
LDH	$\geq 3 \times$ ULN	
BUN	$\geq 30 \text{ mg/dL}$	
Creatinine	$\geq 2.0 \text{ mg/dL}$	
Uric Acid		
Men	$\geq 10.5 \text{ mg/dL}$	
Women	$\geq 8.5 \text{ mg/dL}$	
Bilirubin (total)	$\geq 2.0 \text{ mg/dL}$	
CPK	$\geq 3 \times$ ULN	
Endocrinology		
Prolactin	$>$ ULN	
Hematology		
Hematocrit		
Men	$\leq 37\%$ and decrease of ≥ 3 percentage points from Baseline	
Women	$\leq 32\%$ and decrease of ≥ 3 percentage points from Baseline	
Hemoglobin		
Men	$\leq 11.5 \text{ g/dL}$	
Women	$\leq 9.5 \text{ g/dL}$	
White blood count	$\leq 2,800/\text{mm}^3$ or $\geq 16,000/\text{mm}^3$	
Eosinophils	$\geq 10\%$	
Neutrophils	$\leq 15\%$	
Absolute neutrophil count	$\leq 1,000/\text{mm}^3$	
Platelet count	$\leq 75,000/\text{mm}^3$ or $\geq 700,000/\text{mm}^3$	
Urinalysis		
Protein	Increase of ≥ 2 units	
Glucose	Increase of ≥ 2 units	
Additional Criteria		
Chloride	$\leq 90 \text{ mEq/L}$ or $\geq 118 \text{ mEq/L}$	
Potassium	$\leq 2.5 \text{ mEq/L}$ or $\geq 6.5 \text{ mEq/L}$	
Sodium	$\leq 126 \text{ mEq/L}$ or $\geq 156 \text{ mEq/L}$	
Calcium	$\leq 8.2 \text{ mg/dL}$ or $\geq 12 \text{ mg/dL}$	
Glucose		
Fasting	$\geq 100 \text{ mg/dL}$	
Non-Fasting	$\geq 200 \text{ mg/dL}$	
Total Cholesterol, Fasting	$\geq 240 \text{ mg/dL}$	
LDL Cholesterol, Fasting	$\geq 160 \text{ mg/dL}$	
HDL Cholesterol, Fasting		
Men	$< 40 \text{ mg/dL}$	
Women	$< 50 \text{ mg/dL}$	
Triglycerides, Fasting	$\geq 150 \text{ mg/dL}$	

Appendix 3 Criteria for Identifying ECG Measurements of Potential Clinical Relevance

Variable	Criterion Value ^a	Change Relative to Baseline ^a
Heart Rate	≥ 120 bpm ≤ 50 bpm	increase of ≥ 15 bpm decrease of ≥ 15 bpm
PR	≥ 200 msec	increase of ≥ 50 msec
QRS	≥ 120 msec	increase of ≥ 20 msec
QTcF	> 450 msec (males and females)	

Appendix 4 Adverse Events of Interest

AE Category	Preferred Term
EFFECT ON GLUCOSE	Blood glucose abnormal Blood glucose increased Diabetes mellitus Diabetes mellitus inadequate control Diabetes with hyperosmolarity Diabetic coma Diabetic hyperglycaemic coma Diabetic hyperosmolar coma Diabetic ketoacidosis Diabetic ketoacidotic hyperglycaemic coma Glucose tolerance decreased Glucose tolerance impaired Glucose tolerance test abnormal Glucose urine present Glycosuria Glycosylated haemoglobin increased Hyperglycaemia Hyperglycaemic hyperosmolar nonketotic syndrome Impaired fasting glucose Increased insulin requirement Indeterminate glucose tolerance Insulin resistance Insulin resistant diabetes Insulin tolerance test abnormal Insulin-requiring type 2 diabetes mellitus Ketoacidosis Ketonuria Ketosis Metabolic syndrome Type 1 diabetes mellitus Type 2 diabetes mellitus Urine ketone body present
EFFECT ON LIPIDS	3-hydroxyacetyl-coenzyme A dehydrogenase deficiency Acquired mixed hyperlipidaemia Apolipoprotein Apolipoprotein A-I Apolipoprotein A-I abnormal Apolipoprotein A-I decreased Apolipoprotein A-I increased Apolipoprotein A-I normal Apolipoprotein A-II Apolipoprotein A-II abnormal Apolipoprotein A-II decreased Apolipoprotein A-II increased Apolipoprotein A-II normal Apolipoprotein B Apolipoprotein B abnormal Apolipoprotein B decreased Apolipoprotein B increased

Apolipoprotein B normal
Apolipoprotein B/Apolipoprotein A-1 ratio
Apolipoprotein B/Apolipoprotein A-1 ratio increased
Apolipoprotein C
Apolipoprotein C abnormal
Apolipoprotein E
Apolipoprotein E abnormal
Apolipoprotein E increased
Apolipoprotein abnormal
Apolipoprotein decreased
Apolipoprotein increased
Apolipoprotein normal
Autoimmune hyperlipidaemia
Barth syndrome
Blood cholesterol
Blood cholesterol abnormal
Blood cholesterol decreased
Blood cholesterol esterase increased
Blood cholesterol increased
Blood cholesterol normal
Blood triglycerides
Blood triglycerides abnormal
Blood triglycerides decreased
Blood triglycerides increased
Blood triglycerides normal
Body fat disorder
CANDLE syndrome
Cardiac steatosis
Carnitine
Carnitine abnormal
Carnitine decreased
Carnitine deficiency
Carnitine increased
Carnitine normal
Carnitine palmitoyltransferase deficiency
Carnitine-acylcarnitine translocase deficiency
Cholesterol absorption efficiency decreased
Cholesterosis
Chylomircron decreased
Chylomircron increased
Chylomircrons
Congenital carnitine deficiency
Dyslipidaemia
Epidural lipomatosis
Facial wasting
Familial high density lipoprotein deficiency
Familial hypertriglyceridaemia
Fat redistribution
Fatty acid deficiency
Fatty acid oxidation disorder
Fatty liver alcoholic
Free fatty acids
Free fatty acids abnormal
Free fatty acids decreased

Free fatty acids increased
Gastric xanthoma
HIV lipodystrophy
Hepatic steato-fibrosis
Hepatic steatosis
High density lipoprotein
High density lipoprotein abnormal
High density lipoprotein decreased
High density lipoprotein increased
High density lipoprotein normal
Hyper HDL cholesterolaemia
Hypercholesterolaemia
Hyperchylomicronaemia
Hyperlipidaemia
Hypertriglyceridaemia
Hypo HDL cholesterolaemia
Hypocarnitinaemia
Hypocholesterolaemia
Hypolipidaemia
Hypotriglyceridaemia
Inborn error of lipid metabolism
Intermediate density lipoprotein decreased
Intermediate density lipoprotein increased
Intestinal lipomatosis
Intestinal steatosis
LDL/HDL ratio
LDL/HDL ratio decreased
LDL/HDL ratio increased
Lecithin-cholesterol acyltransferase activity decreased
Lecithin-cholesterol acyltransferase activity increased
Lecithin-cholesterol acyltransferase deficiency
Lipaemia retinalis
Lipaemic index score
Lipid metabolism disorder
Lipid proteinosis
Lipids
Lipids abnormal
Lipids decreased
Lipids increased
Lipids normal
Lipoatrophy
Lipodystrophy acquired
Lipoedema
Lipohypertrophy
Lipomatosis
Lipoprotein (a)
Lipoprotein (a) abnormal
Lipoprotein (a) decreased
Lipoprotein (a) increased
Lipoprotein (a) normal
Lipoprotein abnormal
Lipoprotein deficiency
Lipoprotein increased
Long-chain acyl-coenzyme A dehydrogenase deficiency

Low density lipoprotein
Low density lipoprotein abnormal
Low density lipoprotein decreased
Low density lipoprotein increased
Low density lipoprotein normal
Medium-chain acyl-coenzyme A dehydrogenase deficiency
Mesangiolipidosis
Non-alcoholic steatohepatitis
Non-high-density lipoprotein cholesterol
Non-high-density lipoprotein cholesterol decreased
Non-high-density lipoprotein cholesterol increased
Nonalcoholic fatty liver disease
Pancreatic steatosis
Parotid lipomatosis
Partial lipodystrophy
Phospholipidosis
Phytanic acid increased
Phytosterol level
Phytosterol level increased
Phytosterolaemia
Primary hypercholesterolaemia
Remnant hyperlipidaemia
Remnant-like lipoprotein particles
Remnant-like lipoprotein particles increased
Renal lipomatosis
Renal phospholipidosis
Serum pristanic acid increased
Short-chain acyl-coenzyme A dehydrogenase deficiency
Steatohepatitis
Tangier disease
Thyroid steatosis
Total cholesterol/HDL ratio
Total cholesterol/HDL ratio abnormal
Total cholesterol/HDL ratio decreased
Total cholesterol/HDL ratio increased
Total cholesterol/HDL ratio normal
Trifunctional protein deficiency
Type I hyperlipidaemia
Type II hyperlipidaemia
Type III hyperlipidaemia
Type IIa hyperlipidaemia
Type IIb hyperlipidaemia
Type IV hyperlipidaemia
Type V hyperlipidaemia
Very long-chain acyl-coenzyme A dehydrogenase deficiency
Very low density lipoprotein
Very low density lipoprotein abnormal
Very low density lipoprotein decreased
Very low density lipoprotein increased
Very low density lipoprotein normal
Xanthelasma
Xanthoma
Xanthomatosis
Zieve syndrome

Protocol 331-102-00059

EFFECTS ON WEIGHT

Abnormal weight gain
Body mass index abnormal
Body mass index increased
Obesity
Overweight
Waist circumference increased
Weight fluctuation
Weight increased

EPS

Abnormal involuntary movement scale
Action tremor
Akathisia
Akinesia
Asterixis
Athetosis
Ballismus
Blepharospasm
Bradykinesia
Bradyphrenia
Buccoglossal syndrome
Chorea
Choreoathetosis
Chronic tic disorder
Clumsiness
Cogwheel rigidity
Complex tic
Dopamine dysregulation syndrome
Drooling
Dysarthria
Dyskinesia
Dyskinesia neonatal
Dyskinesia oesophageal
Dyslalia
Dysphonia
Dystonia
Dystonic tremor
Emprosthotonus
Essential tremor
Excessive eye blinking
Extrapyramidal disorder
Facial spasm
Fine motor skill dysfunction
Freezing phenomenon
Fumbling
Gait disturbance
Gait inability
Gaze palsy
Glabellar reflex abnormal
Grimacing
Head titubation
Huntington's disease
Hyperkinesia
Hyperkinesia neonatal
Hypertonia
Hypertonia neonatal

Hypokinesia
Hypokinesia neonatal
Hypokinetic dysarthria
Intention tremor
Laryngeal tremor
Laryngospasm
Meige's syndrome
Micrographia
Mobility decreased
Motor dysfunction
Movement disorder
Muscle contractions involuntary
Muscle contracture
Muscle rigidity
Muscle spasms
Muscle spasticity
Muscle tightness
Muscle tone disorder
Muscle twitching
Musculoskeletal stiffness
Myoclonus
Myotonia
Nuchal rigidity
Oculogyric crisis
Oesophageal spasm
On and off phenomenon
Opisthotonus
Oromandibular dystonia
Oropharyngeal spasm
Parkinson's disease
Parkinson's disease psychosis
Parkinsonian crisis
Parkinsonian gait
Parkinsonian rest tremor
Parkinsonism
Parkinsonism hyperpyrexia syndrome
Periodic limb movement disorder
Pharyngeal dyskinesia
Pharyngeal dystonia
Pleurothotonus
Postural reflex impairment
Postural tremor
Posture abnormal
Posturing
Propulsive gait
Protrusion tongue
Provisional tic disorder
Psychomotor hyperactivity
Rabbit syndrome
Reduced facial expression
Respiratory dyskinesia
Resting tremor
Restless legs syndrome
Restlessness

HAEMATOPOIETIC/LEUKOPENIA

Risus sardonicus
 Saliva altered
 Salivary hypersecretion
 Secondary tic
 Spasmodic dysphonia
 Tardive dyskinesia
 Tic
 Tongue paralysis
 Tongue spasm
 Torticollis
 Torticollis psychogenic
 Tremor
 Tremor neonatal
 Trismus
 Uvular spasm
 Walking disability
 Writer's cramp
 5q minus syndrome
 ABO haemolytic disease of newborn
 ABO incompatibility
 ADAMTS13 activity abnormal
 ADAMTS13 activity assay
 ADAMTS13 activity decreased
 ADAMTS13 activity increased
 ADAMTS13 activity normal
 ADAMTS13 inhibitor screen assay
 Aase syndrome
 Abdominal lymphadenopathy
 Abnormal clotting factor
 Accessory spleen
 Acid haemolysin test
 Acid haemolysin test negative
 Acid haemolysin test positive
 Acquired Von Willebrand's disease
 Acquired amegakaryocytic thrombocytopenia
 Acquired antithrombin III deficiency
 Acquired asplenia
 Acquired complement deficiency disease
 Acquired dysfibrinogenaemia
 Acquired factor IX deficiency
 Acquired factor VIII deficiency
 Acquired factor XI deficiency
 Acquired haemoglobinopathy
 Acquired haemophilia
 Acquired protein S deficiency
 Acquired thalassaemia
 Acral angiokeratoma-like pseudolymphoma
 Activated partial thromboplastin time
 Activated partial thromboplastin time abnormal
 Activated partial thromboplastin time normal
 Activated partial thromboplastin time prolonged
 Activated partial thromboplastin time ratio
 Activated partial thromboplastin time ratio abnormal
 Activated partial thromboplastin time ratio decreased

Activated partial thromboplastin time ratio fluctuation
Activated partial thromboplastin time ratio increased
Activated partial thromboplastin time ratio normal
Activated partial thromboplastin time shortened
Activated protein C resistance
Activated protein C resistance test
Activated protein C resistance test positive
Acute bilineal leukaemia
Acute biphenotypic leukaemia
Acute chest syndrome
Acute erythroid leukaemia
Acute febrile neutrophilic dermatosis
Acute haemolytic transfusion reaction
Acute haemorrhagic oedema of infancy
Acute leukaemia
Acute leukaemia in remission
Acute lymphocytic leukaemia
Acute lymphocytic leukaemia (in remission)
Acute lymphocytic leukaemia recurrent
Acute lymphocytic leukaemia refractory
Acute megakaryocytic leukaemia
Acute megakaryocytic leukaemia (in remission)
Acute monocytic leukaemia
Acute monocytic leukaemia (in remission)
Acute myeloid leukaemia
Acute myeloid leukaemia (in remission)
Acute myeloid leukaemia recurrent
Acute myeloid leukaemia refractory
Acute myelomonocytic leukaemia
Acute promyelocytic leukaemia
Acute undifferentiated leukaemia
Adenoiditis
Administration site lymphadenopathy
Adult T-cell lymphoma/leukaemia
Adult T-cell lymphoma/leukaemia recurrent
Adult T-cell lymphoma/leukaemia refractory
Adult T-cell lymphoma/leukaemia stage I
Adult T-cell lymphoma/leukaemia stage II
Adult T-cell lymphoma/leukaemia stage III
Adult T-cell lymphoma/leukaemia stage IV
Agranulocytosis
Aleukaemic leukaemia
Allergic bronchopulmonary mycosis
Allergic eosinophilia
Alloimmunisation
Alpha-thalassaemia-intellectual deficit syndrome
A megakaryocytic thrombocytopenia
Anaemia
Anaemia Heinz body
Anaemia folate deficiency
Anaemia macrocytic
Anaemia megaloblastic
Anaemia neonatal
Anaemia of chronic disease

Anaemia of malignant disease
Anaemia of pregnancy
Anaemia postoperative
Anaemia splenic
Anaemia vitamin B12 deficiency
Anaemia vitamin B6 deficiency
Anaemic hypoxia
Anaphylactoid syndrome of pregnancy
Anaplastic large cell lymphoma T- and null-cell types
Anaplastic large cell lymphoma T- and null-cell types recurrent
Anaplastic large cell lymphoma T- and null-cell types refractory
Anaplastic large cell lymphoma T- and null-cell types stage I
Anaplastic large cell lymphoma T- and null-cell types stage II
Anaplastic large cell lymphoma T- and null-cell types stage III
Anaplastic large cell lymphoma T- and null-cell types stage IV
Anaplastic large-cell lymphoma
Angiocentric lymphoma
Angiocentric lymphoma recurrent
Angiocentric lymphoma refractory
Angiocentric lymphoma stage I
Angiocentric lymphoma stage II
Angiocentric lymphoma stage III
Angiocentric lymphoma stage IV
Angioimmunoblastic T-cell lymphoma
Angioimmunoblastic T-cell lymphoma recurrent
Angioimmunoblastic T-cell lymphoma refractory
Angioimmunoblastic T-cell lymphoma stage I
Angioimmunoblastic T-cell lymphoma stage II
Angioimmunoblastic T-cell lymphoma stage III
Angioimmunoblastic T-cell lymphoma stage IV
Angiolympoid hyperplasia with eosinophilia
Anisochromia
Anisocytosis
Anti A antibody
Anti A antibody positive
Anti B antibody
Anti B antibody positive
Anti Kell antibody test
Anti Kell antibody test negative
Anti Kell antibody test positive
Anti factor IX antibody
Anti factor IX antibody increased
Anti factor IX antibody negative
Anti factor IX antibody positive
Anti factor V antibody
Anti factor V antibody positive
Anti factor VII antibody positive
Anti factor VIII antibody increased
Anti factor VIII antibody negative
Anti factor VIII antibody positive
Anti factor VIII antibody test
Anti factor X activity
Anti factor X activity abnormal
Anti factor X activity decreased

Anti factor X activity increased
Anti factor X activity normal
Anti factor X antibody
Anti factor X antibody negative
Anti factor X antibody positive
Anti factor XI antibody positive
Anti factor XII antibody positive
Anti factor Xa activity decreased
Anti factor Xa assay normal
Anti-complement antibody
Anti-erythropoietin antibody
Anti-erythropoietin antibody negative
Anti-erythropoietin antibody positive
Anti-prothrombin antibody positive
Anti-thrombin antibody
Antiphospholipid syndrome
Antithrombin III
Antithrombin III abnormal
Antithrombin III decreased
Antithrombin III deficiency
Antithrombin III increased
Aplasia pure red cell
Aplastic anaemia
Application site lymphadenopathy
Aspiration bone marrow
Aspiration bone marrow abnormal
Aspiration bone marrow normal
Asplenia
Atypical haemolytic uraemic syndrome
Atypical lymphocytic lobular panniculitis
Atypical mycobacterial lymphadenitis
Autoimmune anaemia
Autoimmune aplastic anaemia
Autoimmune haemolytic anaemia
Autoimmune heparin-induced thrombocytopenia
Autoimmune lymphoproliferative syndrome
Autoimmune neutropenia
Autoimmune pancytopenia
Autosomal recessive megaloblastic anaemia
Axillary web syndrome
B precursor type acute leukaemia
B-cell aplasia
B-cell lymphoma
B-cell lymphoma recurrent
B-cell lymphoma refractory
B-cell lymphoma stage I
B-cell lymphoma stage II
B-cell lymphoma stage III
B-cell lymphoma stage IV
B-cell prolymphocytic leukaemia
B-cell small lymphocytic lymphoma
B-cell small lymphocytic lymphoma recurrent
B-cell small lymphocytic lymphoma refractory
B-cell small lymphocytic lymphoma stage I

B-cell small lymphocytic lymphoma stage II
B-cell small lymphocytic lymphoma stage III
B-cell small lymphocytic lymphoma stage IV
B-cell type acute leukaemia
B-cell unclassifiable lymphoma high grade
B-cell unclassifiable lymphoma low grade
B-lymphocyte abnormalities
B-lymphocyte count
B-lymphocyte count abnormal
B-lymphocyte count decreased
B-lymphocyte count increased
Babesiosis
Band neutrophil count
Band neutrophil count decreased
Band neutrophil count increased
Band neutrophil percentage
Band neutrophil percentage decreased
Band neutrophil percentage increased
Bandaemia
Banti's syndrome
Basophil count
